**TABLE 12 MANAGEMENT OF NAUSEA/VOMITING**

Grade	Description	Treatment	Dose Modification
≤2	Loss of appetite with or without decreased oral intake. 1 to 5 episodes of vomiting within 24 hours.	
 
Maximize anti-emetic therapy.
 
Consider IV fluid hydration.
 
	None
≥3	Inadequate oral intake. ≥6 episodes of vomiting within 24 hours.	
 
Maximize anti-emetic therapy.
 
Initiate tube feeding, IVF or TPN.
 
	If experienced for ≤72 hours, hold TAK-228 until ≤grade 1, then resume TAK-228 without dose modification. If experienced for >72 hours despite optimal therapy, hold TAK-228 until ≤grade 1, then resume treatment with the dose of TAK-228 reduced by 1 level.

**Prevention/Prophylaxis:**

Prophylactic use of antiemetic, antinausea, and antidiarrheal medications are encouraged and may be used before each TAK-228 dosing as needed throughout the study.

IV=intravenous; IVF=intravenous fluids; TPN=total parenteral nutrition.

**11.6.6 Management of Cardiac Abnormalities**

**Management of Patients With Possible Cardiac Instability**

For patients showing signs of cardiac instability after TAK-228 administration, additional onsite monitoring before clinic discharge should be considered.

**Management of Patients With Left Ventricular Dysfunction**

Guidance on TAK-228 dose modification for patients with left ventricular dysfunction is provided in Table 13.

**TABLE 13 MANAGEMENT OF LEFT VENTRICULAR DYSFUNCTION**

Grade	Description	Dose Modification
1	Asymptomatic decline in: LVEF >15% from baseline values, OR LVEF >10% to 15% from baseline values and is below institution's LLN.	No change; continue TAK-228 at the same dose and schedule.
≥2	Symptomatic cardiac dysfunction/congestive heart failure.	Discontinue treatment.

LLN=lower limit of normal; LVEF=left ventricular ejection fraction.

**Management of Patients with QTc Prolongation**

Guidance on TAK-228 dose modification for patients with prolonged QTc interval is provided in Table 14.

**TABLE 14 MANAGEMENT OF QTc PROLONGATION**

Grade	Description	Treatment	Dose Modification
2	480 msec <QTc <501 msec	Evaluate for other possible causes (e.g., electrolyte disturbance, concomitant medication, etc.).	None; continue TAK-228 at the same dose and schedule.

**TABLE 14 MANAGEMENT OF QTc PROLONGATION**

Grade	Description	Treatment	Dose Modification
≥3	QTc ≥501 msec	Evaluate for other possible causes (e.g., electrolyte disturbance, concomitant medication a ). Consider a formal consult by a cardiologist. Notify the study doctor. Additional ECGs may be performed at intervals that the treating physician deems clinically appropriate until repeated QTc measurements fall or are below the threshold interval that triggered the repeat measurement.	Hold TAK-228. The decision whether to reinitiate TAK-228 with or without dose reduction and additional monitoring in those patients who had asymptomatic prolonged QTc ≥501 msec (grade 3) that has reverted to an acceptable interval, have previously tolerated TAK-228, and appear to have benefitted from treatment with either disease control or response, will be agreed to by the investigator on a case-by-case basis. Patients who experience persistent symptomatic grade 3 or grade 4 QTc prolongation without another cause should permanently discontinue study treatment.

ECG=electrocardiogram; IV=intravenous; msec=milliseconds; QTc=QT interval corrected for heart rate.

aA list of medications known to prolong QTc can be found at <https://www.crediblemeds.org/new-drug-list/>

### **11.6.7 Management of Other Non-hematologic Toxicities (Including Asthenia, Weakness, and Fatigue)**

Guidance on TAK-228 dose modification for patients with other non-hematologic toxicities is provided in Table 15.

**TABLE 15 MANAGEMENT OF OTHER NON-HEMATOLOGIC TOXICITIES (INCLUDING ASTHENIA, WEAKNESS, AND FATIGUE)**

Grade	Description	Treatment	Dose Modification
1	Mild; asymptomatic or mild symptoms; clinical or diagnostic observations only; intervention not indicated.	Initiate appropriate medical therapy and monitor.	If tolerable, then no adjustment is required.
2	Moderate; minimal, local or noninvasive intervention indicated.	Initiate appropriate medical therapy and monitor.	
 
• If tolerable, then no adjustment required.
 
• If toxicity becomes intolerable, hold TAK-228 until recovery to ≤grade 1, then reinitiate at the same dose.
 

≥ 3	Severe or medically significant but not immediately life-threatening; hospitalization or prolongation of hospitalization indicated.		Hold TAK-228 until recovery to ≤grade 1. Reinitiate TAK-228 at dose reduced by 1 level.  Patients who develop grade 4 non-hematological toxicities (with the exception of isolated non-clinically significant laboratory values) should permanently discontinue study treatment, unless they derive clinical benefit, in which case they may be retreated at a reduced dose level after recovery to ≤grade 1 severity.

### **11.6.8 Management of AST/ALT Elevations**

Guidance on TAK-228 dose modification for patients with AST/ALT elevations is provided in Table 16.

**TABLE 16 MANAGEMENT OF AST/ALT ELEVATIONS**

Grade	Description	Treatment	Dose Modification
1	>ULN to 3×ULN	None	None
2	Asymptomatic with levels 3 to 5×ULN; >3×ULN with the appearance of worsening fatigue, nausea, vomiting, right upper quadrant pain or tenderness, fever, rash, or eosinophilia.	
 
Closely monitor LFTs at least weekly or more frequently as indicated.
 
Assess patient for other causes of transaminitis (e.g., past medical history, concomitant medications).
 
	None
3	>5 to 20×ULN; >5×ULN for >2 weeks	Same as for grade 2.	Hold TAK-228 until ≤grade 1; Restart TAK-228 at the same dose. Permanently discontinue study treatment if in combination with grade 2 total bilirubin elevation when alternative causes cannot be identified (i.e., Hy's Law).
4	>20×ULN	Same as for grade 2.	Stop TAK-228 and discontinue patient from the study. Permanently discontinue study treatment if in combination with grade 2 total bilirubin elevation when alternative causes cannot be identified (i.e., Hy's Law).

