**FIGURE 1 STUDY OVERVIEW DIAGRAM**

**TABLE 1 SCHEDULE OF EVENTS**

Visit	Screening a	Baseline b	V1	V2	V3	V4	V5	V6	V7*	EOT
Week	-4 to -3	-2 to -1	1	3	4	6	8	12	16*	
Informed Consent	X									
Inclusion/Exclusion	X									
Demographics	X									
Medical History	X									
Physical Exam c		X	X	X	X	X	X	X	X	X
Height	X									
Weight	X	X	X	X	X	X	X	X	X	X
ECOG PS	X	X	X	X	X	X	X	X	X	X
Vital Signs d	X	X	X	X	X	X	X	X	X	X
12-Lead ECG e		X								X
Hematology f		X	X	X	X	X	X	X	X	X
Clinical Chemistry g		X	X	X	X	X	X	X	X	X
FSH/LH/Estradiol h		X								
Serum Pregnancy ( $\beta$ -hCG) i		X								
Urinalysis j		X	X	X	X	X	X	X	X	X
Fasting Lipid Panel k		X			X		X	X	X	X
Bilateral Mammogram and US l		X								X
Breast MRI m		X								X
Clinical Breast Exam		X			X		X	X	X	X
Concomitant Therapies										Continuous from screening period
Tumor Assessments (RECIST 1:1)		X								X
Biopsy n		X					X			
Tumor Tissue o		X				X				
TAK-228 Administration p										Weekly from day 1, week 1 through day 1, week 16
Tamoxifen Administration p										Continuous daily from day 1, week 1 through day 7, week 16
AEs and SAEs										From ICF signing up to and including 30 days after local treatment q
Pharmacokinetics r										Days 1 and 15

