## 9.3 Duration of Study

Patients will receive TAK-228 QW and tamoxifen QD for 16 weeks. Screening for inclusion in the study will be done within 28 days prior to the day 1 dose of TAK-228 and tamoxifen. Baseline vital signs, labs, physical exam, and biopsy and tumor tissue collection will be done within 7 days prior to the day 1 dose of TAK-228 and tamoxifen. Visits will occur at weeks 1, 3, 4, 6, 8, 12, and 16 and at end of treatment (7 to 10 days after the final dose of study treatment).

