#### 11.1.2 Criteria for Dose Interruption During a Cycle/Visit

TAK-228 should be withheld for treatment-related toxicities that are grade 3 or higher despite supportive treatment per standard clinical practice. If the event resolves to grade 1 (or grade 2 for hyperglycemia or rash) or to baseline values within 3 weeks of interrupting treatment, then the patient may resume study treatment at a dose level reduced by 1 level.

The following non-hematologic toxicities attributed to TAK-228 would not require dose interruption:

- Grade 3 or higher nausea and/or emesis in the absence of optimal antiemetic prophylaxis (optimal antiemetic prophylaxis is defined as an antiemetic regimen that employs both a serotonin type 3 receptor antagonist and a corticosteroid given in standard doses and according to standard schedules)
- Grade 3 or higher diarrhea that occurs in the absence of optimal supportive therapy
- Grade 3 fatigue

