**TABLE 7 TAK-228 DOSE MODIFICATIONS**

Dose Level	TAK-228 Dose	TAK-228 Number of Capsules and Strength
0	30 mg p.o. QW	Six 5 mg capsules
-1	20 mg p.o. QW	Four 5 mg capsules
-2	15 mg p.o. QW	Three 5 mg capsules
-3	10 mg p.o. QW	Two 5 mg capsules

For patients who are unable to tolerate the protocol-specified dosing schedule, dose reductions or interruptions are permitted to manage drug-related toxicities. Patients whose treatment is interrupted or permanently discontinued due to an AE including abnormal laboratory value must be followed at least once a week for 4 weeks and subsequently at 4-week intervals until resolution or stabilization of the event, whichever comes first. Dose interruptions should be reported on the appropriate Dosage Administration case report form (CRF). The maximum time allowed for toxicity-related treatment interruption is 21 days (3 weeks) from the intended dosing day. If treatment interruption is >3 weeks or more than 3 dose reductions are required, the patient must be discontinued from the study treatment. However, they will need to complete the EOT visit within 30 to 40 days after the last dose of TAK-228, and the patient will continue to be followed for toxicity.

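### Table 16, grade 3 AST/ALT row: the Hy's Law stop is printed for grade 2 bilirubin without a ≥ sign, so read literally an unexplained grade 3 bilirubin is not a mandatory stop (minor)

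*Combined protocol and SAP*

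**What the plan says.** Table 16 (section 11.6.8) sets the TAK-228 action by AST/ALT grade. In the grade 3 row the default is to hold until grade 1 or better and then restart at an unchanged dose. One sentence overrides that default: "Permanently discontinue study treatment if in combination with grade 2 total bilirubin elevation when alternative causes cannot be identified". It closes with a parenthetical identifying the condition as Hy's Law. The grade 4 row repeats the sentence, but that row has already stopped TAK-228 and removed the patient from the study.

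Bilirubin has no management table of its own, so two general rules also bear on it:

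- Section 11.1.2: "TAK-228 should be withheld for treatment-related toxicities that are grade 3 or higher despite supportive treatment per standard clinical practice". If the event recovers within 3 weeks, "then the patient may resume study treatment at a dose level reduced by 1 level".
- Table 15 (other non-hematologic toxicities), grade 3 and above: hold until grade 1 or better, then "Reinitiate TAK-228 at dose reduced by 1 level". Patients with grade 4 events "should permanently discontinue study treatment, unless they derive clinical benefit, in which case they may be retreated at a reduced dose level".

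The text below Table 7 caps any hold: "The maximum time allowed for toxicity-related treatment interruption is 21 days (3 weeks) from the intended dosing day".

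**The concern.** A Hy's Law stop should become firmer, or at least no weaker, as bilirubin rises. The printed trigger names a single grade. Followed word for word within the grade 3 AST/ALT row, it ends treatment for an unexplained grade 2 bilirubin but leaves an unexplained grade 3 bilirubin to rules that permit restarting the drug. At stake is whether a patient with suspected drug-induced liver injury could be re-exposed under the written rule, and whether a site that restarted would be in breach of the protocol. The efficacy analysis, sample size and power are not involved.

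**Working it through.** The plan gives no figure to reproduce. The check is a reading of the rules side by side, followed by a dose count.

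**1. Action by bilirubin grade, with AST/ALT at grade 3 and no alternative cause, read literally**

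| Bilirubin | Text that applies | Action |
|---|---|---|
| Grade 2 | Table 16 override | Permanent stop, no exception |
| Grade 3 | Override not met; Table 16 default, Table 15 and section 11.1.2 | Hold; restart possible after recovery |
| Grade 4 | Override not met; Table 15 | Permanent stop by default, with a clinical-benefit exception |

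The middle row is the gap. No other section closes it. The text below Table 7 forces discontinuation only when a hold exceeds 3 weeks or more than three dose reductions are needed. Section 11.12 gives the investigator a right, not a duty, to withdraw a patient for an adverse event.

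**2. Grade 4 AST/ALT row.** TAK-228 stops whatever the bilirubin, so the missing sign changes nothing there.

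**3. Restart dose in the gap.** Table 16's default is the same dose, which is 30 mg for a patient at level 0. Table 15 and section 11.1.2 give one level lower, which is 20 mg (Table 7, level -1). The documents do not say which prevails, so both are carried forward.

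**4. Number of further doses**

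Inputs:

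- Dosing runs "Weekly from day 1, week 1 through day 1, week 16" (Table 1).
- "Visits will occur at weeks 1, 3, 4, 6, 8, 12, and 16 and at end of treatment" (section 9.3).
- The hold is at most 21 days from the intended dosing day, so h = 1 to 3 weekly doses are withheld.

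Assumptions: the patient is at 30 mg, the event is found at the scheduled visit in week v before that week's dose, and dosing resumes in week v + h.

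Further doses = 16 − (v + h) + 1 = 17 − v − h

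| Visit week v | h = 1 | h = 3 |
|---|---|---|
| 3 | 13 | 11 |
| 4 | 12 | 10 |
| 6 | 10 | 8 |
| 8 | 8 | 6 |
| 12 | 4 | 2 |
| 16 | 0 | none left |

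For events at weeks 3 to 12 the range is 2 to 13 doses. On the 20 mg branch that is 2 × 20 = 40 mg to 13 × 20 = 260 mg; on the 30 mg branch, 2 × 30 = 60 mg to 13 × 30 = 390 mg. Under a permanent stop it is 0. These are dose counts for one affected patient, not an estimate of risk.

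**The case against.** The strongest reply is that the sentence explains itself. By naming Hy's Law it says what the condition is, and the only competing reading makes the rule weaker as bilirubin worsens, which nobody would intend. This stands as to meaning: grade 2 is almost certainly a floor. It does not supply the missing threshold. A mandatory stop should be correct in its stated grade and not depend on a parenthetical to repair it.

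A reader might infer that the bare grade is deliberate, because the protocol spells out higher grades elsewhere, as section 11.1.2 does for withholding. The documents do not support that. The same section gives the recovery target for hyperglycemia and rash as a bare grade 2, where Tables 8 and 11 use a ≤ sign for the same recovery. The protocol therefore uses bare grades and inequality signs interchangeably, and drafting habit settles nothing here.

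It can also be said that the case is hard to reach, and this stands. It needs all of the following:

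- grade 3 AST/ALT with unexplained grade 3 bilirubin;
- no sample showing grade 2 bilirubin while AST/ALT is still grade 3, although Table 16 asks for liver tests at least weekly;
- recovery of both within 21 days;
- an investigator who chooses to restart, since section 11.1.2 permits resumption but does not require it.

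The upper end of 13 doses further needs recovery within about a week, a timing the documents neither support nor exclude.

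**Conclusion.** The point holds as a minor wording fault in a safety rule. Read literally, the grade 3 row of Table 16 does not make unexplained grade 3 bilirubin a mandatory permanent stop, and no other section does. At most, an affected patient could receive 2 to 13 further weekly doses at 20 or 30 mg instead of none, on the assumptions stated in the dose count.

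The documents give no frequency for this combination. It should be rare among 35 patients, since entry requires bilirubin no higher than the upper limit of normal (Gilbert's syndrome excepted) and AST/ALT within 1.5 times that limit (section 10.1, criterion 7b).

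A reader might infer that the plan means to rechallenge patients whose liver injury is worsening, or that a definite excess exposure in milligrams follows. Neither is supported. The Hy's Law label points the other way, and the restart dose is unsettled between two rules. Nor does the fault extend to grade 4 AST/ALT. Grade 4 bilirubin stops by default, subject to the clinical-benefit exception in Table 15.

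The conclusion assumes that the table as issued carries no sign before the 2. A lost character cannot be fully excluded but is unlikely: a ≤ sign survives in the same cell, and the phrase is bare in both rows. There is no statistical effect.

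**What to change.** In the grade 3 row of Table 16, insert ≥ so that the trigger reads *grade ≥2 total bilirubin elevation*, leaving the rest of the sentence and the Hy's Law label unchanged. Make the same edit in the grade 4 row for consistency only; it alters no patient's treatment. Optionally add that Table 15's clinical-benefit exception does not apply when this stop is met, which would also cover grade 4 bilirubin.

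The cost is one symbol in each of two rows at the next amendment. Total bilirubin, AST and ALT are already in the chemistry panel drawn at baseline, every visit and end of treatment (Table 1, footnote g), so no test or visit is added.

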**Prevention/Prophylaxis:**

Ensure proper screening of patients for study participation.

LFTs=liver function tests; ULN=upper limit of normal.

**11.6.9 Management of Non-infectious Pneumonitis**

Guidance on TAK-228 dose modification for patients with pneumonitis is provided in Table 17.

**TABLE 17 MANAGEMENT OF NON-INFECTIOUS PNEUMONITIS**

Grade	Description	Treatment	TAK-228 Dose Modification
1	Asymptomatic: Radiographic findings only.	Rule out infection and closely monitor.	None
2	Symptomatic: Not interfering with activities of daily living.	Rule out infection and consider treatment with corticosteroids until symptoms improve to ≤grade 1.	Interrupt TAK-228 
 
When symptoms ≤grade 1, reinitiate TAK-228 at a dose reduced by 1 level. If no recovery within 3 weeks (21 days), then discontinue TAK-228.
 

3	Symptomatic: Interfering with activities of daily living; Requires administration of oxygen.	Rule out infection and consider treatment with corticosteroids until symptoms improve to ≤grade 1.	Interrupt TAK-228 until symptoms resolve to ≤grade 1. 
 
Consider reinitiating TAK-228 at a dose reduced by 1 level.
 
If toxicity recurs at grade 3, discontinue TAK-228.
 

4	Life-threatening: Ventilatory support indicated.	Rule out infection and consider treatment with corticosteroids.	Discontinue TAK-228.

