#### **4.1.4 Rash**

Rash observed in clinical studies of TAK-228 tends to be maculopapular and pruritic and has ranged from grade 1 to 3. For the most part, rash and pruritus improve with antihistamines, topical steroid creams, and/or dose interruption. Some patients have required pulse systemic steroids, dose reduction, and/or study treatment discontinuation.

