## **11.3 Excluded Concomitant Medications and Procedures and Potential DDIs**

The following medications and procedures are prohibited during the study:

- Other investigational agents including mTOR, PI3K, and AKT inhibitors
- Other anticancer therapies including chemotherapy, immunotherapy, radioimmunotherapy, targeted agents, radiation, and surgery (palliative radiation and surgery for preexisting lesions is allowed during the study)
- Systemic corticosteroids (either IV or oral steroids, excluding inhalers), unless necessary for the treatment of TAK-228-related rash.
- Antiepileptic drugs for patients with treated brain metastasis
- Concomitant administration of any PPI (e.g., omeprazole, esomeprazole, pantoprazole, lansoprazole, and rabeprazole) is not permitted during the study. Patients receiving PPI therapy before enrollment must stop using the PPI for 7 days before their first dose of study drugs.

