### 11.12 Termination of Treatment and/or Study Participation

Patients will be informed that they have the right to withdraw from the study at any time for any reason without prejudice to their medical care. The investigator also has the right to withdraw patients from the study for any of the following reasons:

- AE
- Protocol violation
- Lost to follow-up
- Progressive disease
- Study termination
- Other

At the time of withdrawal, all study procedures outlined for the End of Study visit should be completed. The primary reason for the patient's withdrawal from the study should be recorded in the source documents and CRF.

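### Section 11.3 allows IV or oral corticosteroids only for TAK-228-related rash, yet Table 17 advises considering corticosteroids for grade 2 to 4 pneumonitis

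*Combined protocol and SAP*

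**What the plan says.** Section 11.3 opens its list with "The following medications and procedures are prohibited during the study". One item on that list is "Systemic corticosteroids (either IV or oral steroids, excluding inhalers), unless necessary for the treatment of TAK-228-related rash". Inhalers are outside the ban, and rash is the only condition for which IV or oral use is allowed.

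Table 17 in section 11.6.9 covers non-infectious pneumonitis. At grades 2 and 3 the treatment column says to rule out infection and "consider treatment with corticosteroids until symptoms improve" to grade 1 or lower. At grade 4 it again says to consider corticosteroids, with no stated end point. The grade 3 description includes "Requires administration of oxygen", and grade 4 is life-threatening with ventilatory support. No route is given at any grade.

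For rash, section 4.1.4 reports that "Some patients have required pulse systemic steroids, dose reduction, and/or study treatment discontinuation", and Table 11 lists pulsed steroids as an option at grade 3 or higher. The rash exception in 11.3 fits both.

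Corticosteroids appear in one other relevant place. Section 11.1.2 defines optimal antiemetic prophylaxis as "an antiemetic regimen that employs both a serotonin type 3 receptor antagonist and a corticosteroid", given in standard doses and schedules.

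**The concern.** The prohibited-medication list and the toxicity table give incompatible guidance for the same patient. Section 4.1.5 names pneumonitis as a recognised risk of this drug class and calls for early recognition and prompt intervention, so the situation is foreseeable.

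A site that gives an IV or oral steroid under Table 17 departs from 11.3. A site that obeys 11.3 gives up a treatment that Table 17 says to consider, including for a patient on oxygen. Section 11.12 counts a protocol violation among the grounds for withdrawal: "The investigator also has the right to withdraw patients from the study for any of the following reasons". That is a discretionary power, but following the safety guidance should not create a ground for using it.

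**Working it through.** The main point is textual, and no figure in the plan depends on it. Each grade in Table 17 is set against 11.3:

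| Grade | Corticosteroid advice in Table 17 | TAK-228 afterwards | Covered by the 11.3 exception? |
|---|---|---|---|
| 1 | None | Continues | Not applicable |
| 2 | Consider | Restart one dose level lower on recovery; stop if no recovery in 21 days | No |
| 3 | Consider | Restart one level lower may be considered | No |
| 4 | Consider | Discontinued | No |

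Three of the four grades carry corticosteroid advice. In two of those three, TAK-228 may restart. The exception covers none of them.

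**Could other text reconcile the two?**

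- *Permitted medications (11.4).* Covers H2 antagonists, antacids and calcium, CYP1A2 inhibitors and CYP inducers. It does not mention corticosteroids.
- *Pneumonitis warning (4.1.5).* Gives no exception.
- *Order of precedence.* None is stated. Because 11.3 names one toxicity as exempt, the ordinary reading is that others are not.
- *Dose interruption.* The ban runs for the whole study, not only for time on drug, so holding TAK-228 does not lift it.
- *Route.* Table 10 specifies topical or intralesional corticosteroids and Table 11 specifies topical cream or ointment where local treatment is meant. Table 17 has no such limit. This supports a systemic reading without proving it. The oxygen and ventilation descriptions at grades 3 and 4 make it the natural one.

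**How many patients?** The documents give no pneumonitis rate for TAK-228, and section 3.2 does not list it among the most common treatment-emergent events. The rates p below are assumptions:

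- 0.5%: an assumed low value.
- 1%: the upper bound for tamoxifen in Table 4.
- 3%: the grade 3 or 4 rate for everolimus plus exemestane in section 6, which is a different drug, schedule and population.

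Section 13.1.1 allows 20% for screen failure and withdrawal, so n = 35 × 0.80 = 28. Some withdrawals will have been treated, so the number treated lies between 28 and 35.

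Expected cases = n × p. Chance of at least one = 1 − (1 − p)^n. With n = 28:

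| p | Expected cases | Chance of at least one |
|---|---|---|
| 0.5% | 28 × 0.005 = 0.14 | 1 − 0.995^28 = 0.131 |
| 1% | 28 × 0.01 = 0.28 | 1 − 0.99^28 = 0.245 |
| 3% | 28 × 0.03 = 0.84 | 1 − 0.97^28 = 0.574 |

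These count pneumonitis cases, not steroid courses, because treatment is only to be considered.

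**Antiemetic definition (secondary).** Section 11.1.2 uses the corticosteroid-containing regimen as a benchmark: grade 3 or higher nausea or emesis without it does not require interruption. It does not order the regimen. But 11.3 does not permit the steroid by the IV or oral route, so the benchmark cannot be met by those routes. The prevention note to Table 12 says "Prophylactic use of antiemetic, antinausea, and antidiarrheal medications are encouraged and may be used before each TAK-228 dosing" and names no agents.

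**The case against.** The strongest reply is that the contradiction is inferred. Section 11.3 bars only IV and oral steroids, Table 17 names no route, and it says only to consider treatment, so both texts can literally be obeyed. Table 17 is event-specific while 11.3 is a general list, and most clinicians would follow the table. At grade 4 TAK-228 stops, which makes the practical conflict weakest there. Withdrawal under 11.12 would need the treating investigator to choose it. The event is uncommon, and no assumed rate comes from TAK-228.

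Much of this stands as a limit on size:

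- The route is unstated, and the systemic reading is weaker at grade 2, where daily activities are not affected.
- The withdrawal consequence is remote.
- The probabilities are illustrative and carry little weight.
- The antiemetic point is minor. Table 12 holds TAK-228 at grade 3 or higher whether symptoms last up to or beyond 72 hours, so under that table a hold does not depend on the 11.1.2 definition.
- The link between the experience in 4.1.4 and the exception in 11.3 is an inference; neither section cites the other.

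The objection does not remove the conflict. Both texts can be obeyed together only by giving up the systemic option, which is the one that matters for a patient on oxygen or a ventilator. Reading the table as overriding the list requires a precedence rule that the protocol does not contain.

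**Conclusion.** The concern holds. As written, the only therapeutic exception in 11.3 leaves out a toxicity for which the protocol's own management table advises considering corticosteroids at three of four grades. It looks like an omission, since nothing suggests a deliberate decision to withhold steroids for pneumonitis.

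The conclusion assumes that corticosteroids in Table 17 include IV or oral use, which is close to certain at grades 3 and 4 and reasonable at grade 2. The practical conflict is clearest at grades 2 and 3, where the patient may return to TAK-228.

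The case for correction rests on the seriousness of the event and the ease of the remedy, not on frequency. The primary Ki67 analysis has no stated dependence on this point. The verdict does not rely on the antiemetic point.

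**What to change.** 1. In section 11.3, extend the exception from TAK-228-related rash to TAK-228-related pneumonitis, or more generally to any toxicity managed under section 11.6.
2. In Table 17, state that systemic corticosteroids are allowed at grades 2 to 4.
3. Separately, either exempt short-course antiemetic corticosteroids in 11.3 or take the corticosteroid out of the 11.1.2 definition of optimal antiemetic prophylaxis.

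The cost is protocol wording only, with no change to sample size, procedures or analysis.
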